Advancement to higher combination dose levels during the escalation phase will occur after an evaluation of safety and tolerability by the Dose Committee. The proposed continual reassessment method (CRM) will generate dose combination recommendations. The model estimates the probability of dose limiting toxicities (DLTs) in Cycle 1 (C1) at each candidate combination dose level to determine the dose combination to treat the next cohort. The MTD is selected as the combination associated with the highest posterior probability of DLT rating within the target interval of 25% - 35% and which have been used to treat at least 6 participants.

During escalation, a minimum of 3 participants on a combination dose level are required to be DLT evaluable to render a decision to proceed to the next dose level. A 4th participant, if available, may enroll onto the escalation dose before the first 3 participants have completed the DLT evaluation. DLT events for all participants at a given combination dose level will be entered into the CRM model and assessed by the Study Dose Committee. The first cycle (28 days) constitutes the DLT assessment period. Parallel Dose-Escalation Cohorts may be allowed.

***Dose-Expansion Component:*** After the Dose-Escalation Component has ended and the RP2D is determined, a Dose-Expansion cohort of up to 90 participants (including those already enrolled at this dose in the Dose-Escalation and Expansion cohorts) will be enrolled at the RP2D. In this Dose-Expansion cohort, up to 15 participants in each of the 6 genotypic/histotypic cohorts will be enrolled.

Moreover, once the Dose-Escalation Component has reached a threshold of activity based on clinically meaningful reduction in tumor burden at a dose with acceptable toxicity, additional participants may possibly be enrolled at dose levels prior to the determination of RP2D. The Dose Committee will determine whether clinically meaningful reduction has been achieved (eg,  $\geq 30\%$  reduction in the sum of longest diameters of target lesions or a lesser diminution with a preponderance of clinical evidence of benefit). See 'Dose-Escalation and Expansion Committee Charter' for more information.

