#### 4.1.1.3. Dose-Escalation Rules

Dose escalation will be guided using a CRM model ([Appendix 10](#)) to determine the MTD of the combination of RMC-4630 and cobimetinib. This CRM is an adaptive dose escalation approach based on a Bayesian statistical model to assess the MTD for drug combinations as a function of their doses. [REDACTED]

[REDACTED] The MTD is selected as the combination associated with the highest posterior probability of DLT rating within the target interval of 25% - 35% with a target DLT rate of 30%, and which have been used to treat at least 6 participants. If alternative dosing schedule(s) are evaluated, a separate CRM model will be set up using the same modeling structure but potentially different parameters according to the updated prior knowledge of the safety of the alternative dosing schedule(s).

During the escalation period, participants will be enrolled in a series of cohorts for each combination dose level. A minimum of 3 participants are required on a combination dose level to be DLT evaluable and to render a decision to proceed to the next dose level. A 4th participant, if available, may enroll onto the escalation dose before the first 3 participants have completed the DLT evaluation. However, in the case a 4th patient is enrolled in a cohort, dose escalation decision will take place after the first 3 patients have completed the DLT assessment period.

Once the DLT status of the 4th patient is available, and if this patient experiences a DLT after dose escalation decision and enrollment of the subsequent dose level, the Sponsor will rerun the Bayesian model and the Dose Committee will re-evaluate the dose escalation recommendation and continuation of treatment at the subsequent dose level. If a participant experiences a DLT, additional participants will be enrolled at that dose. The cohort at the MTD will include at least 6 participants.

A participant will be DLT non-evaluable in either of the following 2 scenarios where a replacement participant(s) will be enrolled:

1. Receives less than 75% of planned dose of cobimetinib (miss  $\geq 3$  doses of cobimetinib on DID2 intermittent schedule and  $\geq 6$  doses of cobimetinib on 21 on/7 off schedule within the DLT window) for reasons other than toxicity
2. Misses 3 or more consecutive or non-consecutive doses of RMC-4630 within the DLT window for reasons other than toxicity

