**4.2.1.3. Dose-Escalation Rules**

In the event a participant discontinues treatment prior to completion of the first cycle (DLT window), receives less than 75% of planned dose of osimertinib (defined as missing 8 or more consecutive or non-consecutive doses of osimertinib), receives less than 75% of planned dose of RMC-4630 (defined as missing 3 or more consecutive or non-consecutive doses of RMC-4630) for reasons other than toxicity, a replacement participant will be enrolled for a minimum of 3 DLT evaluable participants.

The Dose Committee will be responsible for reviewing and evaluating the safety, efficacy data and other relevant available information (PK or biomarker data) during the DLT period and provide a final decision regarding the next dose escalation level. The RP2D will be determined

by the Sponsor based on the totality of the information available at all dose levels and should not exceed the MTD. If 2 or more DLTs are observed beyond the DLT assessment period (ie, a delayed DLT) within a Dose-Escalation Cohort, further enrollment may be stopped pending safety analysis of the events. These events will not affect the determination of the MTD but will be used in determining the appropriate RP2D. Further details on the Dose Committee are provided in [Section 8.3.6](#). The Sponsor will determine regarding opening the Dose-Expansion Component.

The ISMC will conduct regular safety data reviews of emergent data from the RMC-4630 program as well as ad hoc emergent safety data reviews for all participants across RMC-4630 trials.

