### 6.6. Dose Modification

#### 6.6.1. Dose Modification Rules

A 28-day cycle will be maintained, and dose interruption will be noted in the 28-day cycle schedule.

In the Dose-Escalation cohorts, there will be no dose reductions or modifications during C1, 28-day DLT assessment period unless a DLT has occurred. After C1 and in the Dose-Expansion cohorts, if a dose reduction is recommended, then the combination dose level should be the previous lower dose level considered to be tolerable in prior participants receiving that dose. If the previous lower dose level comprised of two parallel cohorts (ie, two combination dose levels), the investigator and sponsor Medical Monitor may choose one of two lower combination dose level based on the participant’s medical and study drugs history.

- [REDACTED]
- [REDACTED]
- [REDACTED]
- [REDACTED]
- [REDACTED]

[REDACTED]

[REDACTED]

[REDACTED]

Two types of dose modifications are allowed, “dose interruption” and “dose level reduction.” The decision will be per investigator, according to the dose modification criteria and guidelines outlined in [Section 6.6](#). Any allowed dose modification and any deviation from the intended dose (missed doses or overdoses due to participant error) should be documented on the dose electronic Case Report Form (eCRF).

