**Table 15 Population Definitions**

Population	Description
Enrolled	All participants who sign an ICF and meet eligibility criteria
Treated	All participants who take at least 1 dose of study intervention
Evaluable	
Evaluable for DLT: All participants in the treated population who have completed the DLT period or who have discontinued due to AEs or death (unless relationship to RMC-4630 and cobimetinib can be ruled out) prior to the end of the DLT period. In addition, participants must receive at least 75% of planned dose (not miss <math>\geq 3</math> doses of RMC-4630 and cobimetinib on D1D2 intermittent schedule and <math>\geq 6</math> doses of cobimetinib on 21 on/7 off schedule, and <math>\geq 8</math> doses of osimertinib within the DLT window for reasons other than toxicity). This population will be the primary population for fitting the dose-toxicity model.
 
Evaluable for efficacy: All participants with measurable disease at baseline, who take at least 1 dose of study intervention and underwent one post-baseline response assessment or who die or had clinical progression prior to first post-baseline response assessment

Safety	All participants who take at least 1 dose of study intervention

Abbreviations: AE, adverse event; DLT, dose-limiting toxicity; ICF, informed consent form.

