#### 9.4.2. Safety Analyses

All DLT modeling will be performed on the DLT-evaluable population. All other safety analyses will be performed on the Safety Population. The statistical analysis methods to be used during the safety analyses by endpoint is presented in Table 17.

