**Table 17 Safety Analyses**

Endpoint	Statistical Analysis Methods
Primary	Summaries of AEs, SAEs, and AEs leading to treatment discontinuation and dose modification, changes in laboratory test results and changes in vital signs, and DLT rate
Secondary	Not applicable
Exploratory	Will be described in the statistical analysis plan finalized before database lock

Abbreviations: AE, adverse event; DLT, dose-limiting toxicity; SAE, serious adverse event.

AEs and SAEs will be displayed by combination dose level.

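### As written, Table 15 can drop a participant with an observed Cycle 1 DLT from the dose-finding data, and its causality clause omits osimertinib

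*Combined protocol and SAP*

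**What the plan says.** **Who is evaluable.** Table 15 (Section 9.3) gives two routes into the DLT-evaluable set. A treated participant must have "completed the DLT period or who have discontinued due to AEs or death (unless relationship to RMC-4630 and cobimetinib can be ruled out"). A second condition is added: at least 75% of planned dose, counting only misses that are not due to toxicity. The limits are 3 missed doses for RMC-4630 and for cobimetinib on D1D2, 6 for cobimetinib on 21/7, and 8 for osimertinib. The row calls this the primary population for fitting the dose-toxicity model.

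**What the set is used for.** Section 9.4.2: "All DLT modeling will be performed on the DLT-evaluable population". All other safety analyses use the Safety Population. Table 17 lists among the primary safety summaries "changes in laboratory test results and changes in vital signs, and DLT rate" without naming a population for the last item.

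**Who is replaced.** In the cobimetinib arm (Section 4.1.1.3), one trigger for non-evaluability and replacement is: "Misses 3 or more consecutive or non-consecutive doses of RMC-4630 within the DLT window for reasons other than toxicity". In the osimertinib arm (Section 4.2.1.3), early discontinuation or too few doses, "for reasons other than toxicity, a replacement participant will be enrolled for a minimum of 3 DLT evaluable participants". Neither rule makes an exception for a participant who has already had a DLT.

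**What points the other way.** The cobimetinib synopsis (Section 1.1.1, Overall Design) says "DLT events for all participants at a given combination dose level will be entered into the CRM model". Section 6.6.2 treats certain participants with a Grade 3 DLT as having had it at the original dose.

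**Attribution in the osimertinib arm.** Section 4.2.1.2 counts toxicity related to study treatment, without restricting it to RMC-4630. Appendix 3 requires a causality assessment for both study drugs.

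**The concern.** A DLT is the outcome that dose finding counts. Once it has been observed, the participant's result is known, and later exposure adds nothing to that fact. Completion and exposure rules exist to stop an under-treated participant from being counted as DLT-free. Table 15 applies them to everyone, so an observed toxicity can be removed because of what happened afterwards. Replacement then puts a new participant in its place.

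The causality clause is a separate fault. The row sets a missed-dose limit for osimertinib, so it governs that arm, yet it tests relationship only to RMC-4630 and cobimetinib. Cobimetinib is not given in that arm, so the test turns on RMC-4630 alone.

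At stake is the input to the CRM and to the mTPI-2 count, where decisions rest on 3 to 6 participants. In the cobimetinib arm, two analysts following different sections would fit different data to the same cohort. Read literally, Section 9.4.2 also puts Table 17's DLT rate on the Safety Population, so the report could show a DLT that the dose-finding data do not contain.

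**Working it through.** **1. The plan's own figure.** The missed-dose limits reproduce the 75% rule over a 28-day cycle:

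| Drug and schedule | Planned doses | Still passes | Fails |
|---|---|---|---|
| RMC-4630 twice weekly; cobimetinib D1D2 | 8 | miss 2: 6/8 = 75.0% | miss 3: 5/8 = 62.5% |
| Cobimetinib 21/7 | 21 | miss 5: 16/21 = 76.2% | miss 6: 15/21 = 71.4% |
| Osimertinib daily | 28 | miss 7: 21/28 = 75.0% | miss 8: 20/28 = 71.4% |

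**2. Can the case arise?** In the escalation cohorts, Section 6.6.1 says "there will be no dose reductions or modifications during C1, 28-day DLT assessment period unless a DLT has occurred", so a participant with a DLT may stay on treatment. RMC-4630 on D1D2 falls on Days 1, 2, 8, 9, 15, 16, 22 and 23. Suppose a DLT on Day 8 and withdrawal of consent before dosing on Day 15:

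- The participant did not complete the window and did not stop for an AE or death, so the first condition fails.
- Four of 8 doses (Days 15, 16, 22, 23) are missed for a non-toxicity reason, so the exposure rule fails (limit: 3).
- The participant is replaced in either arm and is outside the modeling set.

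**3. The causality clause.** Suppose a Cycle 1 stop for a DLT attributed to osimertinib alone. It is a DLT under Section 4.2.1.2, but literally excluded by Table 15, because relationship to RMC-4630 has been ruled out and cobimetinib was not given. If Section 4.2.1.3 replaces only non-toxicity exits, nobody takes the place. A cohort of 3 then has 2 evaluable participants against a stated minimum of 3.

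**4. Effect on the mTPI-2 call (osimertinib arm).** The target interval is not visible, so it is assumed: targets 20, 25, 30 and 33%, with lower and upper margins of 2, 3 or 5 points each, giving 4 × 3 × 3 = 36 intervals. With x DLTs in n, the posterior is Beta(1+x, 1+n−x). The unit interval is cut into pieces of the target width, and the piece with the highest posterior probability per unit length gives the call (E escalate, S stay, D de-escalate).

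| Assumed interval | 1/3 | 0/3 | 2/6 | 1/6 |
|---|---|---|---|---|
| 15–25% | D | E | D | S |
| 20–30% | D | E | D | E |
| 25–35% | S | E | S | E |
| 28–38% | S | E | S | E |

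Over all 36 intervals:

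- 1/3 kept, against 0/3 after loss and DLT-free replacement: D to E in 24, S to E in 12.
- 2/6 kept, against 1/6: D to E in 20, S to E in 12, D to S in 4. The call is less cautious in all 36.

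**5. How often.** Let p be the true DLT rate and a the assumed chance that a participant with a DLT later leaves for a non-toxicity reason. On the 20–30%, 25–35% and 28–38% intervals only 0/3 reads escalate. A first cohort of 3 therefore flips when it had at least one DLT, all its DLTs are lost, and no replacement has one:

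P = (1−p)³ × [(1 + pa)³ − 1]

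| | a = 10% | a = 20% |
|---|---|---|
| p = 30% | 0.343 × (1.03³ − 1) = 3.2% | 0.343 × (1.06³ − 1) = 6.5% (0.0655) |
| p = 40% | 0.216 × (1.04³ − 1) = 2.7% | 0.216 × (1.08³ − 1) = 5.6% |

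**6. Average bias.** This depends on who leaves. If 20% of participants with a DLT and 5% of those without leave, a true 30% appears as 0.30×0.80 / (0.30×0.80 + 0.70×0.95) = 26.5%. With equal leaving rates there is no average bias, though observed DLTs are still lost.

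**7. Cobimetinib arm.** No change of decision can be computed, because the CRM appendix is not visible.

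**The case against.** - **Hidden text may cover it.** Appendix 10, Table 6 and part of the osimertinib rules in Section 4.2 are not visible, and Section 9.4 defers full escalation details to a simulation report. An exception there cannot be excluded. It would, however, still conflict with Table 15 and Section 9.4.2.
- **The synopsis sentence may only mean that the 4th participant counts too.** Its position allows that reading, which would soften the contradiction. It would also leave the cobimetinib arm with no sentence that keeps the DLT.
- **Completing the DLT period is undefined.** If it means 28 days of observation, a participant who stops drug but stays in follow-up meets the first condition. The exposure rule still fails for one who misses 3 or more RMC-4630 doses for non-toxicity reasons. After a DLT many misses would be toxicity-related and excused, which narrows the case.
- **The 2-of-3 shortfall rests on one reading of Section 4.2.1.3.** If early discontinuation for any reason leads to replacement, there is no shortfall, but the DLT is still lost.
- **The comparator matters.** Against 1/4 (DLT kept and a replacement also treated), 15 of the 36 intervals already read escalate and nothing changes; the call still changes in 21. Under the proposed rule the participant is not replaced, so 1/3 is the relevant comparison.
- **Safeguards.** Section 4.1.1.3 says "If a participant experiences a DLT, additional participants will be enrolled at that dose". The Dose Committee decides on all available safety data (Section 8.3.6), and at least 6 participants are needed at the MTD. First imaging follows Cycle 2 (Section 8.1), so Cycle 1 exits for progression should be uncommon. These limit the harm but do not define the model input.

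**Conclusion.** The concern holds on the text as it stands. Table 15 is wrong as written rather than merely short of detail: applied literally, it removes an observed DLT from the only set allowed for DLT modeling, and its causality clause does not fit the osimertinib arm that it governs.

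The practical size is modest. The event needs a Cycle 1 DLT followed in the same window by an exit or missed doses for another reason. Under the assumed exit rates it flips about 3 to 7% of first osimertinib cohorts of 3 to escalate. When it does happen, the change is always toward a less cautious call in the 1/3 and 2/6 cases examined. These figures rest on an assumed target interval, a Beta(1,1) prior and assumed exit rates, because the documents show none of them.

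The causality gap is probably rare. A relationship to RMC-4630 must be ruled out although overlapping toxicity is considered possible (Section 2.3.1.5), and entry requires prior tolerance of osimertinib (Section 5.1). It should be corrected, but it does not by itself undermine the trial.

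**What to change.** 1. State in Table 15 and in Sections 4.1.1.3 and 4.2.1.3 that any treated participant with a Cycle 1 DLT is DLT-evaluable and is not replaced, whatever doses were received. Apply the completion and 75% exposure rules only to participants without a DLT.
2. In the causality clause, refer to any study drug of the participant's arm.
3. Name the population for the DLT rate in Table 17.
4. Reconcile the synopsis sentence on CRM input with Table 15, Section 9.4.2 and the two replacement rules.

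The cost is wording only. Keeping every DLT while replacing DLT-free early exits tilts the estimated rate slightly upward, the cautious direction. With a fraction d of non-toxicity exits and uniform DLT and exit times, a true 30% is read as p(1−d/2) / [p(1−d/2) + (1−p)(1−d)]:

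- d = 10%: 0.285 / (0.285 + 0.63) = 31.1%
- d = 20%: 0.27 / (0.27 + 0.56) = 32.5%

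If every DLT precedes the exit, the upper bound is p / [p + (1−p)(1−d)], which is 32.3% and 34.9%.

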### 9.4. Statistical Analyses

The statistical analysis plan will be developed and finalized before database lock. This section is a summary of the planned statistical analyses of the primary and secondary endpoints. The full details of the escalation and expansion rules, including prior distributions for the dose-toxicity model, simulations, and operating characteristics, will be documented in separate statistical simulation report.

#### 9.4.1. Efficacy Analyses

The statistical analysis methods to be used during the efficacy analyses by endpoint is presented in [Table 16](#).

**Table 16 Efficacy Analyses**

Endpoint	Statistical Analysis Methods
Primary	Not applicable
Secondary	
ORR is defined as the proportion of participants who achieve a CR or PR per RECIST v1.1. ORR and the corresponding 95% two-sided confidence interval will be derived.
 
DOR is defined as the interval from the first documentation of CR or PR to the earlier of first documentation of definitive disease progression or death due to any cause, whichever occurs first. Participants who are still alive and free from progression at the time of data cutoff date, are lost to follow-up, have discontinued from the study, or have initiated subsequent anticancer therapy will be censored at the last adequate tumor assessment. The Kaplan-Meier method will be used to estimate PFS and DOR curves and corresponding quartiles. Kaplan-Meier median will be calculated with a 2-sided 95% confidence interval.
 
Pharmacokinetics assessed by noncompartmental methods and summarized by descriptive statistics (mean or geometric mean, standard deviation, coefficient of variation, minimum, and maximum).

Exploratory	
Will be described in the statistical analysis plan finalized before database lock.
 
Absolute and percentage changes of pharmacodynamic assessments at baseline and during treatment.

Abbreviations: CR, complete response; DOR, duration of response; ORR, objective response rate; PR, partial response; RAS-MAPK, RAS-mitogen-activated protein kinase; RECIST v1.1, Response Evaluation Criteria in Solid Tumors, Version 1.1.

The secondary efficacy endpoints of ORR and DOR will be summarized for participants enrolled at the RP2D. If available, genotyping results from the central laboratory will supersede those from local tests for primary and secondary endpoints. Local results may be included in exploratory analyses.

PK parameter estimates, including but not limiting to the ones listed below, will be determined when possible for RMC-4630 and cobimetinib:

- $C_{max}$  (observed)
- $T_{max}$  (observed)
- $AUC_{0-t}$  and  $AUC_{inf}$
- $t_{1/2}$
- Accumulation ratio

Unless otherwise specified, the PK parameters will be estimated based on noncompartmental analysis methods. These estimates will be summarized descriptively by dose cohort. All PK parameters will be computed using actual elapsed time calculated relative to dose administration.

Dose proportionality across dose levels will be characterized by plotting  $C_{max}$  and AUC versus dose. Exploratory analyses may be performed to evaluate the relationship between the estimated PK parameters and PDs, selected safety, biomarker, or clinical effect endpoints.

The PK and PD analyses will be presented in a separate report that may be integrated into the main clinical study report.

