### 9.1. Statistical Hypotheses

There are no formal hypotheses to be tested in this study.

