### 9.2. Sample Size Determination

Both arms of the study will include two components: a Dose-Escalation Component and a Dose-Expansion Component consisting of 6 genotypic/histotypic cohorts.

Doses for both RMC-4630 and cobimetinib will vary in dose escalation component of arm 1. Dose escalation recommendations will be conducted using a CRM model for RMC-4630 and cobimetinib arm ([Appendix 10](#)). [Table 1](#) illustrates sample size estimation based on “Scenario 1” depicted in [Figure 2](#). The study is expected to enroll approximately 144 participants as follows:

- Up to 42 participants during the Dose-Escalation Component, assumes 7 total combination dose cohorts (RMC-4630 dosed twice weekly on D1, D4 or D1, D2 with cobimetinib dosed once daily on 21/7 schedule; RMC-4630 and cobimetinib dosed twice weekly on D1, D2) with 3 to 6 participants per dose. The MTD cohort will enroll at least 6 participants.
- After reaching threshold of activity and achieving DLT clearance at a dose level, at least 24 additional participants may be enrolled during expansion prior to RP2D for a maximum 12 participants per dose level (assumes 4 combination dose expansion cohorts).

- Up to 90 participants (15 per class of mutation x 6 strata) will be enrolled at RP2D (combination dose level 4a). Assuming 12 participants are already enrolled during dose escalation and expansion into cohort that will be declared RP2D, additional 78 participants will be enrolled into RP2D cohort.

The primary objective of this study is safety evaluation. The objective the efficacy evaluation is to generate data which will enable a preliminary estimation of the treatment effect. The treatment effect will be interpreted in the clinical context of specific genotypes and histotypes. The target disease stabilization rate is 30%. If 5 out of 15 participants have achieved disease stabilization, the observed disease stabilization rate would be 33% where the lower limit of the 95% CI is 12%, which excludes a null rate of 10%. A sample size of 15 will provide preliminary evidence of efficacy of RMC-4630 and cobimetinib. Replacement of efficacy unevaluable participants at RP2D may be considered.

With a sample size of 144 study participants, the probability of observing 1 or more instances of a specific AE with a true incidence rate of 1%, 2%, or 5% is 76%, 95%, or >99%, respectively.

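### Dose proportionality is characterised only by plots; a power-model slope with a confidence interval, from the same data, would show how far they support it

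*Combined protocol and SAP*

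**What the plan says.** Section 9.4.1 (text after Table 16) reads "Dose proportionality across dose levels will be characterized by plotting" Cmax and AUC versus dose. It names no model, slope, interval or criterion.

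The rest of the readable PK plan is as follows.

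- The Secondary row of Table 16: "Pharmacokinetics assessed by noncompartmental methods and summarized by descriptive statistics", with the mean or geometric mean, standard deviation, coefficient of variation and range.
- The text below the table, on the RMC-4630 and cobimetinib parameters: "These estimates will be summarized descriptively by dose cohort".
- Optional further work: "Exploratory analyses may be performed to evaluate the relationship between the estimated PK parameters and PDs", and to safety, biomarker or clinical effect endpoints. Regression of exposure on dose is not listed.

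Section 9.4 says of itself: "This section is a summary of the planned statistical analyses of the primary and secondary endpoints". A SAP is to be finalised before database lock, and PK and PD results go into a separate report. Section 9.1 states: "There are no formal hypotheses to be tested in this study".

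**The concern.** A plot shows whether mean exposure rises roughly with dose. It does not give the slope or say how well the data determine it. With few participants per dose and a modest dose range, a wide set of slopes can sit behind a picture that looks proportional, and a report could call exposure dose proportional on data too thin to support the word.

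The same table gives the objective response rate and the Kaplan-Meier medians 95% intervals, so estimation with an interval is already the study's approach. Dose proportionality is the exception. At stake is how the PK result is worded and read. PK is one of several inputs to the RP2D (Section 4.1, below Figure 6) and to opening expansion (Section 8.3.6).

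**Working it through.** The protocol gives no figure for dose proportionality, so there is none to reproduce. The check asks how well a slope could be determined.

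**Inputs from the documents**
- RMC-4630 80 mg: starting dose in the cobimetinib arm, on D1 and D4 (synopsis, Overall Design).
- RMC-4630 140 mg: final expansion dose of that arm, on D1 and D2 (Section 6.1.1), and starting dose of the osimertinib arm (Section 6.1.2).
- 12 participants per dose: the cap for each dose combination level in expansion before the RP2D (synopsis, Dose-Expansion Component).
- Escalation cohorts: "Up to 42 participants during the Dose-Escalation Component, assumes 7 total combination dose cohorts", with 3 to 6 participants per dose (Section 9.2).
- RP2D: "Up to 90 participants (15 per class of mutation x 6 strata) will be enrolled at RP2D" (Section 9.2).

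**Assumptions not in the documents**
- Between-participant CV of 30%, 50% or 70%.
- One first-dose PK value per participant, and PK sampled in everyone counted.
- Log-normal exposure with equal variance at both doses.

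The two doses sit on different schedules, so the illustration applies to first-dose exposure only.

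**Formulas.** Model: ln(parameter) = a + b ln(dose), where b = 1 is proportionality. The log-scale SD is sqrt(ln(1 + CV²)). The standard error of b is SD / sqrt(Sxx), with Sxx the sum of squared deviations of ln(dose). The 90% half-width is t(0.95, n − 2) × SE.

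**Numbers for 12 and 12.** ln(140/80) = 0.560. Each point lies 0.280 from the mean, so Sxx = 24 × 0.2798² = 1.879 and its square root is 1.371. t(0.95, 22) = 1.717.

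| CV (assumed) | Log SD | SE of b | 90% half-width | 90% CI if estimate = 1 | Exposure ratio for a 1.75-fold dose |
|---|---|---|---|---|---|
| 30% | 0.294 | 0.214 | 0.37 | 0.63 to 1.37 | 1.42 to 2.15 |
| 50% | 0.472 | 0.345 | 0.59 | 0.41 to 1.59 | 1.26 to 2.43 |
| 70% | 0.631 | 0.461 | 0.79 | 0.21 to 1.79 | 1.12 to 2.72 |

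The last column is 1.75 raised to each limit; exact proportionality would give 1.75.

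**Sensitivity, all at 50% CV**
- 6 and 6: Sxx = 0.940, t(0.95, 10) = 1.812, half-width 0.88.
- 12 at 80 mg and 90 at 140 mg: Sxx = (12 × 90/102) × 0.5596² = 3.316, SE = 0.472/1.821 = 0.259, t(0.95, 100) = 1.660, half-width 0.43 (0.57 to 1.43).
- 12 and 12 over an assumed threefold range: the half-width scales as 1/ln(ratio), so 0.59 × 0.560/1.099 = 0.30.

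**What the interval does not mean.** Slopes of 0.4 and 1.6 are (1.6 − 0.4)/0.345 = 3.5 standard errors apart at 50% CV (5.6 at 30%, 2.6 at 70%). An estimate of 0.4 at 50% CV would have a 90% interval of about −0.19 to 0.99, which excludes 1.6.

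**The case against.** The case for leaving the text alone has several parts.

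- **Descriptive study.** There are no formal hypotheses, and the protocol claims only to characterise proportionality. This stands against a pass/fail test. It does not count against an estimate with an interval.
- **Numbers already accompany the plots.** Means and CVs by dose cohort will be reported. That is true, but they do not give the slope or its uncertainty.
- **Detail may follow.** Section 9.4 is a summary, Section 8.5 is redacted, and a SAP and a PK report are to come. So plotting can be called the only method in the readable text, and no more. Still, Section 9.4.1 does choose a method, and nothing readable promises another.
- **The illustration may be pessimistic.** Dose-level tables are blacked out, intermediate RMC-4630 levels are allowed, and the RP2D group may be far larger than 12. All of this stands, and it is why the figures are labelled illustrative.
- **Mixed schedules.** The 80 and 140 mg doses in the cobimetinib arm are on D1,D4 and D1,D2. The figures therefore do not describe a steady-state fit within one schedule.

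A reader might also infer two stronger points, and neither is supported. The first is that the data could not tell a slope of 0.4 from one of 1.6. The arithmetic above shows the reverse: those values are only the ends of an interval centred on 1. The second is that an unquantified plot puts dose decisions at risk. Section 8.3.6 bases dosing of the next cohort on safety data. PK enters the opening of expansion and the RP2D as one input among several, with no mention of proportionality. Section 6.1.1 already states the final expansion dose for the cobimetinib arm.

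**Conclusion.** The point holds as a minor one. On the readable text, dose proportionality rests on plots alone, with no slope and no measure of its uncertainty, although the data collected would give both. In the illustration an estimate of 1 carries a 90% half-width of 0.37 at 30% CV and 0.59 at 50% CV, so apparent proportionality could coexist with exposure rising between about 1.3-fold and 2.4-fold over a 1.75-fold dose range at 50% CV. The size depends on the assumed CVs, on the two readable doses and on 12 sampled participants at each. It could be larger with escalation cohorts alone and smaller with a wider dose range or more RP2D participants. No effect on the RP2D or on any dosing decision is shown.

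**What to change.** Add to Section 9.4.1, or to the SAP and PK report plan, beside the plots:

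- Fit ln(parameter) = a + b ln(dose) for Cmax and AUC, and report b with its 90% confidence interval as a descriptive estimate, not a pass/fail test. Do this for RMC-4630 and, where more than one dose is given, for cobimetinib.
- For first-dose exposure, use Cycle 1 Day 1 Cmax and AUC over a common interval that ends before the second dose (about 24 hours on D1,D2), pooled across RMC-4630 schedules.
- For steady-state parameters, fit within schedule, so that dose and schedule are not confounded.
- State the dose range and the number of participants behind each slope.

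The cost is a few lines of PK programming, with no extra samples, visits or participants. The drawback is that the interval may be wide; if so, that is the information the plot leaves out.
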